11.9 Publication of Results

All manuscripts, abstracts, or other modes of presentation arising from the results of the study must be reviewed and approved in writing by the sponsor in advance of submission pursuant to the terms and conditions set forth in the executed Clinical Trial Agreement between the sponsor/CRO and the institution/investigator. The review is aimed at protecting the sponsor's proprietary information existing either at the date of the commencement of the study or generated during the study.

The detailed obligations regarding the publication of any data, material results, or other information generated or created in relation to the study shall be set out in the agreement between each investigator and the sponsor or CRO, as appropriate.

11.10 Disclosure and Confidentiality

The contents of this protocol and any amendments and results obtained during the study should be kept confidential by the investigator, the investigator's staff, and the IRB/IEC and will not be disclosed in whole or in part to others, or used for any purpose other than reviewing or performing the study, without the written consent of the sponsor. No data collected as part of this study will be used in any written work, including publications, without the written consent of the sponsor. These obligations of confidentiality and non-use shall in no way diminish such obligations as set forth in either the Confidentiality Agreement or Clinical Trial Agreement executed between the sponsor/CRO and the institution/investigator.

All persons assisting in the performance of this study must be bound by the obligations of confidentiality and non-use set forth in either the Confidentiality Agreement or Clinical Trial Agreement executed between the institution/investigator and the sponsor/CRO.

11.11 Discontinuation of Study

The sponsor reserves the right to discontinue the study for medical reasons or any other reason at any time. If a study is prematurely terminated or suspended, the sponsor will promptly inform the investigators/institutions and regulatory authorities of the termination or suspension and the reason(s) for the termination or suspension. The IRB/IEC will also be informed promptly and provided the reason(s) for the termination or suspension by the sponsor or by the investigator/institution, as specified by the applicable regulatory requirement(s).

The investigator reserves the right to discontinue the study should his/her judgment so dictate. If the investigator terminates or suspends a study without prior agreement of the sponsor, the investigator should inform the institution where applicable, and the investigator/institution should promptly inform the sponsor and the IRB/IEC and provide the sponsor and the IRB/IEC with a detailed written explanation of the termination or suspension. Study records must be retained as noted above.

11.12 Subject Insurance and Indemnity

The sponsor will provide insurance for any subjects participating in the study in accordance with all applicable laws and regulations.

12 APPENDICES

Appendix 1 Sponsor's Grading for Laboratory Values

Sponsor's Grading for Laboratory Values

	Grade 1	Grade 2	Grade 3	Grade 4
BLOOD/BONE MARROW				
Hemoglobin	<LLN – 10.0 g/dL <LLN – 100 g/L <LLN – 6.2 mmol/L	<10.0 – 8.0 g/dL <100 – 80 g/L <6.2 – 4.9 mmol/L	<8.0 g/dL <80 g/L <4.9 mmol/L; transfusion indicated	life-threatening consequences; urgent intervention indicated
Leukocytes (total WBC)	<LLN – 3.0×10 ⁹ /L <LLN – 3000/mm ³	<3.0 – 2.0×10 ⁹ /L <3000 – 2000/mm ³	<2.0 – 1.0×10 ⁹ /L <2000 – 1000/mm ³	<1.0×10 ⁹ /L <1000/mm ³
Lymphocytes	<LLN – 800/mm ³ <LLN – 0.8×10 ⁹ /L	<800 – 500/mm ³ <0.8 – 0.5×10 ⁹ /L	<500 – 200/mm ³ <0.5 – 0.2×10 ⁹ /L	<200/mm ³ <0.2×10 ⁹ /L
Neutrophils	<LLN – 1.5×10 ⁹ /L <LLN – 1500/mm ³	<1.5 – 1.0×10 ⁹ /L <1500 – 1000/mm ³	<1.0 – 0.5×10 ⁹ /L <1000 – 500/mm ³	<0.5×10 ⁹ /L <500/mm ³
Platelets	<LLN – 75.0×10 ⁹ /L <LLN – 75,000/mm ³	<75.0 – 50.0×10 ⁹ /L <75,000 – 50,000/mm ³	<50.0 – 25.0×10 ⁹ /L <50,000 – 25,000/mm ³	<25.0×10 ⁹ /L <25,000/mm ³
METABOLIC/LABORATORY				
Albumin, serum- low (hypoalbuminemia)	<LLN – 3 g/dL <LLN – 30 g/L	<3 – 2 g/dL <30 – 20 g/L	<2 g/dL <20 g/L	life-threatening consequences; urgent intervention indicated
Alkaline phosphatase	>ULN – 2.5×ULN if baseline was normal; 2.0 – 2.5×baseline if baseline was abnormal	>2.5 – 5.0×ULN if baseline was normal; >2.5 – 5.0×baseline if baseline was abnormal	>5.0 – 20.0×ULN if baseline was normal; >5.0 – 20.0×baseline if baseline was abnormal	>20.0×ULN if baseline was normal; >20.0×baseline if baseline was abnormal
ALT	>ULN – 3.0×ULN if baseline was normal; 1.5 – 3.0×baseline if baseline was abnormal	>3.0 – 5.0×ULN if baseline was normal; 3.0 – 5.0×baseline if baseline was abnormal	>5.0 – 20.0×ULN if baseline was normal; >5.0 – 20.0×baseline if baseline was abnormal	>20.0×ULN if baseline was normal; >20.0×baseline if baseline was abnormal
AST	>ULN – 3.0×ULN if baseline was normal; 1.5 – 3.0×baseline if baseline was abnormal	>3.0 – 5.0×ULN if baseline was normal; 3.0 – 5.0×baseline if baseline was abnormal	>5.0 – 20.0×ULN if baseline was normal; >5.0 – 20.0×baseline if baseline was abnormal	>20.0×ULN if baseline was normal; >20.0×baseline if baseline was abnormal
Bilirubin (hyperbilirubinemia)	>ULN – 1.5×ULN if baseline was normal; 1.0 – 1.5×baseline if baseline was abnormal	>1.5 – 3.0×ULN if baseline was normal; 1.5 – 3.0×baseline if baseline was abnormal	>3.0 – 10.0×ULN if baseline was normal; 3.0 – 10.0×baseline if baseline was abnormal	>10.0×ULN if baseline was normal; >10.0×baseline if baseline was abnormal
Calcium, serum-low (hypocalcemia)	<LLN – 8.0 mg/dL <LLN – 2.0 mmol/L Ionized calcium <LLN – 1.0 mmol/L	<8.0 – 7.0 mg/dL <2.0 – 1.75 mmol/L Ionized calcium <1.0 – 0.9 mmol/L; symptomatic	<7.0 – 6.0 mg/dL <1.75 – 1.5 mmol/L Ionized calcium <0.9 – 0.8 mmol/L; hospitalization indicated	<6.0 mg/dL <1.5 mmol/L Ionized calcium <0.8 mmol/L; life-threatening consequences

Sponsor's Grading for Laboratory Values

	Grade 1	Grade 2	Grade 3	Grade 4
Calcium, serum-high (hypercalcemia)	>ULN – 11.5 mg/dL >ULN – 2.9 mmol/L Ionized calcium >ULN - 1.5 mmol/L	>11.5 – 12.5 mg/dL >2.9 – 3.1 mmol/L Ionized calcium >1.5 - 1.6 mmol/L; symptomatic	>12.5 – 13.5 mg/dL >3.1 – 3.4 mmol/L Ionized calcium >1.6 - 1.8 mmol/L; hospitalization indicated	>13.5 mg/dL >3.4 mmol/L Ionized calcium >1.8 mmol/L; life-threatening consequences
Cholesterol, serum-high (hypercholesterolemia)	>ULN – 300 mg/dL >ULN – 7.75 mmol/L	>300 – 400 mg/dL >7.75 – 10.34 mmol/L	>400 – 500 mg/dL >10.34 – 12.92 mmol/L	>500 mg/dL >12.92 mmol/L
Creatinine	>ULN – 1.5×ULN	>1.5 - 3.0×baseline; >1.5 – 3.0×ULN	>3.0×baseline; >3.0 – 6.0×ULN	>6.0×ULN
GGT (γ -glutamyl transpeptidase)	>ULN – 2.5×ULN if baseline was normal; 2.0 - 2.5 x baseline if baseline was abnormal	>2.5 – 5.0×ULN if baseline was normal; >2.5 - 5.0 x baseline if baseline was abnormal	>5.0 – 20.0×ULN if baseline was normal; >5.0 - 20.0 x baseline if baseline was abnormal	>20.0×ULN if baseline was normal; >20.0 x baseline if baseline was abnormal
Glucose, serum-high (hyperglycemia)	Abnormal glucose above baseline with no medical intervention	Change in daily management from baseline for a diabetic; oral antiglycemic agent initiated; workup for diabetes	Insulin therapy initiated; hospitalization indicated	life-threatening consequences; urgent intervention indicated
Glucose, serum-low (hypoglycemia)	<LLN – 55 mg/dL <LLN – 3.0 mmol/L	<55 – 40 mg/dL <3.0 – 2.2 mmol/L	<40 – 30 mg/dL <2.2 – 1.7 mmol/L	<30 mg/dL <1.7 mmol/L life-threatening consequences; seizures
Phosphate, serum-low (hypophosphatemia)	Laboratory finding only and intervention not indicated	Oral replacement therapy indicated	Severe or medically significant but not immediately life-threatening; hospitalization or prolongation of existing hospitalization indicated	life-threatening consequences
Potassium, serum-high (hyperkalemia)	>ULN – 5.5 mmol/L	>5.5 – 6.0 mmol/L	>6.0 – 7.0 mmol/L hospitalization indicated	>7.0 mmol/L life-threatening consequences
Potassium, serum-low (hypokalemia)	<LLN – 3.0 mmol/L	<LLN – 3.0 mmol/L; symptomatic; intervention indicated	<3.0 – 2.5 mmol/L hospitalization indicated	<2.5 mmol/L life-threatening consequences
Sodium, serum-high (hypernatremia)	>ULN – 150 mmol/L	>150 – 155 mmol/L; intervention initiated	>155 – 160 mmol/L hospitalization indicated	>160 mmol/L life-threatening consequences
Sodium, serum-low (hyponatremia)	<LLN – 130 mmol/L	125-129 mmol/L and asymptomatic	<125 – 129 mmol/L symptomatic; 120-124 mmol/L regardless of symptoms	<120 mmol/L life-threatening consequences

Sponsor's Grading for Laboratory Values

	Grade 1	Grade 2	Grade 3	Grade 4
Triglyceride, serum-high (hypertriglyceridemia)	150 – 300 mg/dL 1.71 – 3.42 mmol/L	>300 – 500 mg/dL >3.42 – 5.7 mmol/L	>500 – 1000 mg/dL >5.7 – 11.4 mmol/L	>1000 mg/dL >11.4 mmol/L life-threatening consequences
Uric acid, serum-high (hyperuricemia)	>ULN without physiologic consequences	N/A	>ULN with physiologic consequences	life-threatening consequences

ALT = alanine aminotransferase (serum glutamic pyruvic transaminase), AST = aspartate aminotransferase (serum glutamic oxaloacetic transaminase), N/A = not applicable, LLN = lower limit of normal, ULN = upper limit of normal, WBC = white blood cell.

Based on Common Terminology Criteria for Adverse events (CTCAE) Version 5.0. Published: 27 Nov 2017.

PROTOCOL SIGNATURE PAGE

Study Protocol Number: E2814-G000-103

Study Protocol Title: An Open-Label Phase 1b/2 Study to Assess Safety and Target Engagement of E2814 in Subjects with Mild to Moderate Cognitive Impairment due to Dominantly Inherited Alzheimer's Disease

Investigational Product Name: E2814

IND Number: 139378

EudraCT Number: 2020-005728-12

SIGNATURES

Authors:

PPD

Date

Study Director and Medical Monitor

PPD

Eisai Inc

PPD

Date

Clinical Pharmacologist

PPD

Eisai Ltd.

PPD

Date

Primary Statistician

PPD

Eisai Ltd

INVESTIGATOR SIGNATURE PAGE

Study Protocol Number: E2814-G000-103

2 LIST OF ABBREVIATIONS AND DEFINITIONS OF TERMS

Abbreviation	Term
ADA	anti-drug antibody
AE	adverse event
ALQ	above the limit of quantification
ATC	anatomical therapeutic class
AUC _(0-inf)	area under the concentration-time curve from zero time (pre-dose) extrapolated to infinite time
AUC _(0-t)	area under the concentration-time curve from zero time (pre-dose) to time of last quantifiable concentration
BLQ	below the limit of quantification
BMI	body mass index
C _{max}	maximum observed concentration
CRF	case report form
CSF	cerebrospinal fluid
C-SSRS	Columbia-Suicide Severity Rating Scale
CTCAE	Common Terminology Criteria for Adverse Events
CV	coefficient of variation
DIAD	Dominantly Inherited Alzheimer's Disease
ECG	electrocardiogram
LLOQ	lower limit of quantification
MedDRA	Medical Dictionary for Regulatory Activities
MTBR	microtubule binding region
NAb	Neutralizing antibody
NCA-MNL	Eisai Non-compartmental Pharmacokinetic Analysis Manual
PT	preferred term
PD	pharmacodynamic(s)
PK	pharmacokinetic(s)
Q4W	every 4 weeks
SAP	statistical analysis plan
SD	standard deviation
SI	Système International
SOC	system organ class

Abbreviation	Term
TE	target engagement
t_{max}	time at which the highest drug concentration occurs
$t_{1/2}$	terminal elimination phase half-life
TEAE	treatment-emergent adverse event
TEMAV	treatment-emergent markedly abnormal laboratory value
TLG	tables, listings, and graphs
ULOQ	upper limit of quantification
WHO	World Health Organization

3 INTRODUCTION

The purpose of this statistical analysis plan (SAP) is to describe the procedures and the statistical methods that will be used to analyze and report results for Eisai Protocol E2814-G000-103 (Amendment 04).

3.1 Study Objectives

3.1.1 Primary Objectives

The primary objectives of the study were:

- To assess the safety and tolerability of intravenous (IV) infusions of E2814 in subjects with Dominantly Inherited Alzheimer's Disease (DIAD)
- To evaluate target engagement (TE) of E2814 on microtubule binding region (MTBR)-tau species in CSF in subjects with DIAD

[figure not shown]
3.1.2 Secondary Objectives

The secondary objectives of the study were:

- To assess the pharmacokinetics (PK) of E2814 in serum, plasma, and cerebrospinal fluid (CSF)
- To assess the immunogenicity (production of anti-E2814 antibody) of E2814
- To assess the effect of E2814 on CSF, blood, and imaging biomarkers

3.1.3 Exploratory Objectives

The exploratory objectives of the study were:

3.2 Overall Study Design and Plan

E2814-G000-103 was an open-label Phase 1b/2 study to evaluate the safety and TE of E2814 on MTBR-tau species in CSF following IV infusions of E2814 in DIAD subjects. Subjects in this study were confirmed mutation positive for genes known to be associated with DIAD. The mutations in presenilin 1 (*PSEN1*), presenilin 2 (*PSEN2*) and amyloid precursor protein (*APP*) that are associated with DIAD have very high penetrance (near 100%).

The study consisted of 2 Cohorts (A and B).

Cohort A consisted of 2 phases: A Pretreatment Phase consisting of a Screening Period and a Treatment Phase consisting of 3 periods: 1b, 2, and Follow Up.

Cohort B was to consist of a Pretreatment Phase and a Treatment Phase consisting of 2 periods (52-week Treatment Period and 12-week Follow Up Period).

4 DETERMINATION OF SAMPLE SIZE

No formal sample size calculations were performed. For this Phase 1b/2 study, up to 8 subjects in Cohort A and up to 5 subjects in Cohort B were considered adequate to evaluate the initial safety and PK in symptomatic DIAD subjects and to establish evidence of TE.

5 STATISTICAL METHODS

All descriptive statistics for continuous variables will be reported using mean, standard deviation (SD), median, minimum and maximum. Categorical variables will be summarized as number (percentage) of subjects.

5.1 Study Endpoints

All endpoints were measured in both Cohort A and Cohort B.

5.1.1 Efficacy Endpoints

- Change from baseline in cognitive and clinical assessments

5.1.2 Safety Endpoints

- Incidence of treatment-emergent adverse events (TEAEs) and serious adverse events (SAEs), laboratory parameters, vital signs, and ECGs

5.1.3 Pharmacokinetic (PK) Endpoint(s)

- Serum and plasma PK parameters following dosing on Days 1 and 85
- CSF E2814 concentrations.

5.1.4 Pharmacodynamic (PD) Endpoint(s)

- Change from baseline in CSF free and bound MTBR-tau and total MTBR-tau post-treatment
- Change from baseline in CSF biomarkers ^{CCI} [REDACTED]
- Change from baseline in tau PET signal

5.2 Study Subjects

5.2.1 Definitions of Analysis Sets

The Safety Analysis Set is the group of all allocated subjects who received at least 1 dose of study treatment. At least 1 laboratory, vital sign, or ECG measurement obtained subsequent to at least 1 dose of study treatment is required for inclusion in the analysis of each specific parameter. To assess change from baseline, a baseline measurement is also required. This is the analysis population used for all safety analyses which will be based on as-treated principle.

The Pharmacokinetic Analysis Set is the group of subjects who received at least 1 dose of test drug and had sufficient PK data to derive at least 1 PK parameter.

The Pharmacodynamic Analysis Set is the group of subjects who received at least 1 dose of study drug and had sufficient PD data to derive at least 1 PD parameter.

The definition of these analysis sets is the same for both the Phase 1b (Cohort A) and Phase 2 (Cohort A and Cohort B) Treatment Periods; actual determination of these analysis sets will be made separately for each study period. Data from Cohort A and B will be presented combined. In other words, there will one Safety Analysis Set, one Pharmacokinetic Analysis Set and one Pharmacodynamic Analysis Set.

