- The Phase 1b Treatment Period will initially allow 8 subjects to receive open-label treatment with 3 IV infusions of 750 mg E2814 every 4 weeks (Q4W) over 12 weeks. Subjects will check into the clinic on the day before dosing but will not be required to stay in the clinic overnight on Day -1 to Day 2, they may instead stay overnight at a nearby hotel and return to the clinic the next day. In addition, subjects will have outpatient visits on Days 15, 29, and 57. On conclusion of the Phase 1b Treatment Period, on Day 84, subjects will check into the clinic and will undergo safety assessments. Subjects will not be required to stay in the clinic overnight on Day 84 to Day 86, they may instead stay overnight at a nearby hotel and return to the clinic the next day. A CSF sample will be collected for assessment of TE and CSF concentrations of E2814 on Day 1 and Day 84. Subjects will then progress to the Phase 2 Treatment Period. Subjects who withdraw from the Phase 1b Treatment Period for reasons other than safety may be replaced.
- The Phase 2 Treatment Period will allow subjects who tolerated the 750 mg dose of E2814 and completed all assessments in the Phase 1b Treatment Period to receive a further 96 weeks of IV E2814 at an initial dose of 1500 mg Q4W for at least 3 doses (12 weeks) followed by a dose of 3000 mg Q4W for at least 3 doses (12 weeks), followed by a dose of 4500 mg Q4W for the remaining weeks. (revised per Amendments 01 and 02)

- CCI

■

■

Following the in-clinic visit CCI, all subsequent visits will be outpatient visits and CCI

[figure not shown]
(revised per Amendments 01 and 02)

CCI

Cohort B (revised per Amendment 03)

Cohort B consists of 2 phases: A Screening Phase and a Treatment Phase consisting of 2 periods: 52-week Treatment Period and 12-week Follow Up Period.

CCI

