9.1.2.2 Cohort B (revised per Amendment 03)

All subjects in Cohort B will be administered 3000 mg of E2814 Q4W for up to 52 weeks. All visits will be outpatient or home infusion visits and will occur Q4W for the duration of the study. A CSF sample will be collected at baseline, Week 24, and Week 52. Samples will be used to analyze PD effects of E2814 on biomarkers associated with AD. The

concentrations of E2814 in postdose samples will also be assessed. Subjects will also undergo safety MRI, tau PET scans, and cognitive assessment at Visit 2, Week 24, and the End of Study/Early Termination Visit. For subjects who discontinue early, early termination CSF collection and tau PET scan will be performed, unless these assessments were performed within the previous 3 months.

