9.3 Selection of Study Population

Up to 13 subjects (up to 8 subjects in Cohort A and up to 5 subjects in Cohort B) will be enrolled at approximately 4 or more sites in the US and UK. Subjects who do not meet all of the inclusion criteria or who meet any of the exclusion criteria will not be eligible to receive study drug. (revised per Amendment 03)

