9.7.1.8 Safety Analyses

Evaluation of safety will be performed on the Safety Analysis Set. Safety data that will be evaluated include AEs, clinical laboratory results, vital signs, ECGs, C-SSRS, and physical examinations. Safety data from the Phase 1b period of Cohort A will be summarized separately from the Phase 2 Treatment Period of Cohort A and Cohort B. TEAEs will be summarized by dose. (revised per Amendment 03)

Descriptive statistics (eg, mean, SD, median, minimum, and maximum for continuous variables, and the number and percent for categorical variables) of the laboratory, vital signs, and ECGs, and changes from baseline will be evaluated by dose.

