5.6 Safety Analyses

All safety analyses will be performed on the Safety Analysis Set. Safety data, presented by dose, will be summarized using descriptive statistics (eg, n, mean, standard deviation, median, minimum, maximum for continuous variables; n [%] for categorical variables). Safety variables include TEAEs, clinical laboratory parameters, vital signs, and 12-lead

ECG results. Study Day 1 for all safety analyses is defined as the date of the first dose of study drug.

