5.6.2 Adverse Events

The AE verbatim descriptions (investigator terms from the CRF) will be classified into standardized medical terminology using the Medical Dictionary for Regulatory Activities (MedDRA). Adverse events will be coded to the MedDRA (Version 27) lower level term (LLT) closest to the verbatim term. The linked MedDRA preferred term (PT) and primary system organ class (SOC) will also be captured in the database.

A treatment-emergent adverse event (TEAE) is defined as an AE that emerged during treatment, having been absent at pretreatment (Baseline) or

- Reemerged during treatment, having been present at pretreatment (Baseline) but stopped before treatment, or
- Worsened in severity during treatment relative to the pretreatment state, when the AE is continuous.

During treatment is defined as the period between the administration of study drug and up to 113 days after the last study drug dose. Only those AEs that are treatment emergent will be included in summary tables. All AEs, treatment emergent or otherwise, will be presented in subject data listings.

The TEAEs will be summarized by dose. The incidence of TEAEs will be reported as the number (percentage) of subjects with TEAEs by SOC and PT. A subject will be counted only once within a SOC and PT, even if the subject experienced more than 1 TEAE within a specific SOC and PT. The number (percentage) of subjects with TEAEs will also be summarized by maximum severity (mild, moderate, or severe).

The number (percentage) of subjects with treatment-related TEAEs will be summarized by SOC and PT. Treatment-related TEAEs include those events considered by the investigator to be related to study treatment.

Adverse events will be summarized on the Safety Analysis Set. The number of adverse events, number of subjects with adverse events, and incidence (%) will be calculated by dose and overall. To obtain the incidence (%), the number of subjects with at least 1 event and the percentage of subjects with adverse events by system organ class (SOC) and by preferred term (PT) in the Safety Analysis Set will be calculated.

Separate listings will be provided for subjects with deaths, SAEs, and AEs leading to discontinuation.

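### With the cohorts combined and safety shown by dose, the 3000 mg column mixes titrated Cohort A subjects with direct-start Cohort B subjects and describes neither group

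*SAP*

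**What the plan says.** On presentation, SAP 5.2.1 says "Data from Cohort A and B will be presented combined" and provides for a single Safety Analysis Set. SAP 5.6 adds "Safety data, presented by dose, will be summarized using descriptive statistics", and SAP 5.6.2 says that AE "incidence (%) will be calculated by dose and overall". SAP 5.3.2 plans no subgroup analyses, and no SAP safety table is described as split by cohort.

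On how subjects come to 3000 mg, the Protocol Synopsis (Study Design, Cohort A) reads "The Phase 2 Treatment Period will allow subjects who tolerated the 750 mg dose of E2814 and completed all assessments in the Phase 1b". Those subjects go on to higher doses, with 1500 mg for at least three doses, then 3000 mg for at least three doses, then 4500 mg. Protocol 9.1.2.2 says of the other cohort: "All subjects in Cohort B will be administered 3000 mg of E2814 Q4W for up to 52 weeks".

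On numbers, Protocol 9.3 says "Up to 13 subjects (up to 8 subjects in Cohort A and up to 5 subjects in Cohort B) will be enrolled". Subjects who leave Phase 1b for non-safety reasons may be replaced; those removed during Phase 2 may not (Protocol 9.5.5).

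Protocol 9.7.1.8 comes closest to a split: "Safety data from the Phase 1b period of Cohort A will be summarized separately from the Phase 2 Treatment Period of Cohort A and Cohort" (the last word refers to the second cohort). It sets Phase 1b apart but does not clearly set Cohort A at 3000 mg apart from Cohort B. For disposition and demographics, by contrast, Protocol 9.7.1.3 and 9.7.1.4 ask for results overall and by cohort.

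**The concern.** TEAE and SAE incidence is a primary endpoint, and 3000 mg is the only dose at which pooling the cohorts changes a column. The two groups in that column differ in three ways.

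- **History.** Cohort A subjects have passed a 750 mg tolerability requirement and further dosing. Cohort B subjects have no lower dose first.
- **Time at the dose.** Cohort A may have as few as 3 doses at 3000 mg; Cohort B has up to 52 weeks. A crude percentage of subjects with at least one event rises with time at risk.
- **Attribution.** A Cohort A event may follow a recent change of dose. SAP 5.6.2 sets a TEAE window ending 113 days after the last dose, but gives no rule for assigning an event to a dose level.

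The Protocol revision history (Amendment 03) explains Cohort B as a way to learn more about safety and biomarkers at 3000 mg. Only Cohort B shows what happens when the first E2814 infusion is 3000 mg. That bears on infusion reactions, the one study-specific AE in Protocol 9.5.1.4.3. In a pooled column this information cannot be seen, and nothing in the table would tell the reader so.

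**Working it through.** **Inputs.**
- Maximum subjects: 8 in Cohort A and 5 in Cohort B (Protocol 9.3); 8 + 5 = 13, as stated.
- Doses at 3000 mg in Cohort A: at least 3 (Synopsis, Study Treatments). The visible text sets no upper limit, so 6 is shown as an alternative.
- Doses in Cohort B: every 4 weeks for 52 weeks, 52/4 = 13 if treatment is completed.
- Event rates: the plan gives none. Every rate below is an assumption.

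**1. Weight of Cohort A.** 8/13 = 61.5% of the 3000 mg denominator if all reach it; 6/11 = 54.5% if six do; 4/9 = 44.4% if four do.

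**2. Pooled percentage.** Pooled = (nA·pA + nB·pB)/(nA + nB). With nA = 8, nB = 5 and pB = 40%, a Cohort A rate half as large gives (8 × 0.20 + 5 × 0.40)/13 = 27.7%. At pA/pB = 0.75, 1 and 1.25 the pooled value is 33.8%, 40.0% and 46.2%. The pooled figure can therefore fall on either side of the Cohort B rate.

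**3. Unequal exposure alone.** Assume the same constant per-dose risk h in both cohorts and no selection: h = 1 − (1 − pB)^(1/13), pA = 1 − (1 − h)^d for d doses in Cohort A. For pB = 40%, h = 3.85%. With d = 3, pA = 11.1% and pooled = (8 × 0.111 + 5 × 0.40)/13 = 22.2%.

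| Cohort B rate | Doses in A | Cohort A rate | Pooled |
|---|---|---|---|
| 20% | 3 | 5.0% | 10.8% |
| 20% | 6 | 9.8% | 13.7% |
| 40% | 3 | 11.1% | 22.2% |
| 40% | 6 | 21.0% | 28.3% |
| 60% | 3 | 19.1% | 34.8% |
| 60% | 6 | 34.5% | 44.3% |

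**4. Selection alone.** Assume 30% of subjects are susceptible, with TEAE risk at 3000 mg of 80% against 20% in the rest. Then pB = 0.3 × 0.8 + 0.7 × 0.2 = 38%. If a fraction f of susceptible subjects leaves before 3000 mg, the susceptible share among those remaining is 0.3(1 − f)/(1 − 0.3f), and nA = 8(1 − 0.3f).

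| f | nA | Cohort A rate | Pooled |
|---|---|---|---|
| 0 | 8.0 | 38.0% | 38.0% |
| 0.25 | 7.4 | 34.6% | 36.0% |
| 0.5 | 6.8 | 30.6% | 33.7% |
| 1 | 5.6 | 20.0% | 28.5% |

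In these examples unequal exposure lowers the pooled rate more than selection does.

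**5. What a split would show.** With assumed counts of 1/8 and 2/5, the pooled table reads 3/13 = 23.1% (Clopper-Pearson 95% interval 5.0–53.8%). The split reads 12.5% (0.3–52.7%) for Cohort A and 40.0% (5.3–85.3%) for Cohort B.

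**The case against.** The case against has real weight. The study has at most 13 subjects and no hypothesis test. All AEs are listed by subject, with separate listings for deaths, SAEs and discontinuations (SAP 5.6.2), and doses and duration at each dose level are tabulated per subject (SAP 5.6.1). A careful reader could rebuild the split, and once split the columns hold 8 and 5 subjects with very wide intervals. The shells are in a separate document (SAP 11), so the single column is inferred. SAP 5.6.3 to 5.6.5 describe laboratory, vital-sign and ECG summaries by visit; only the general line in 5.6 puts them by dose.

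A reader might also infer something stronger: that the 3000 mg incidence is diluted because Cohort A was selected on the outcome. The documents do not support that.
- The requirement is tolerating 750 mg, an earlier and related outcome, not freedom from a TEAE at 3000 mg.
- Selection has no effect unless subjects actually drop out for tolerability before 3000 mg.
- Carry-over from lower doses, later disease stage or the missing attribution rule could raise the Cohort A rate.
- The extreme case, 2/5 in Cohort B printing as 2/13, needs all eight Cohort A subjects to be present while selection has removed all their risk. Selection works by removing subjects from the denominator, so those two conditions conflict.
- Nor does the primary objective (Protocol 8.1) single out direct start at 3000 mg.

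What remains is that listings let a reader repair the incidence table but do not correct it. The SAP text read as written (combined cohorts, by dose, no subgroups) instructs no split. Its remark that analysis sets are determined separately by study period does not help either, because SAP 5.2.1 places Cohort B together with Cohort A's Phase 2.

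**Conclusion.** The point holds as one of presentation and interpretation. The 3000 mg percentage pools titrated, previously tolerant and possibly briefly exposed subjects with subjects who receive only 3000 mg for up to a year. It describes neither group and may understate the direct-start incidence. Cohort A can carry up to 62% of the denominator.

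Neither the size nor the direction of any distortion can be fixed from the documents. Under constant per-dose risk and 3 versus 13 doses, the pooled figure is a little over half the Cohort B figure across assumed Cohort B rates of 20% to 60%. Under the selection model it runs from no change to 28.5% against 38%. The conclusion rests on the inferred column layout and on the two cohorts differing as described, not on any assumed rate. It should be changed, because the correction is cheap and concerns a primary endpoint.

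**What to change.** In SAP 5.2.1 and 5.6, show 3000 mg as two columns in the TEAE and SAE summaries, and in any other safety summary presented by dose: 'Cohort A 3000 mg (after lower doses)' and 'Cohort B 3000 mg (no lower dose first)'. Give each its own denominator, and either subject-time at 3000 mg or an exposure-adjusted rate. The split alone leaves the two crude percentages non-comparable when time at the dose differs.

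State how a Cohort A event is assigned to a dose level. Footnote the number of Cohort A subjects who did not reach each dose, by reason. Do not report a pooled 3000 mg percentage as the 3000 mg incidence. Make the same split explicit in Protocol 9.7.1.8.

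Three texts need reconciling at the same time.
- SAP 5.2.1 says both that sets are determined separately by study period and that there is one of each.
- SAP 7 reports no changes to the planned analyses, although SAP 5.2.2 and 5.2.4 omit the by-cohort disposition and demographics that Protocol 9.7.1.3 and 9.7.1.4 require.
- Protocol 9.4.1 describes the opening Phase 2 dose differently from the Synopsis, so the Cohort A label is kept general here until the sponsor settles the text.

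The cost is SAP and protocol wording, one extra column in the shells and some exposure arithmetic on data already collected. The downside is columns of at most 8 and 5 subjects, which are descriptive only.
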